We will conduct a clinical trial of our Small Steps intervention which is described below under **Small Steps Intervention Design**. Briefly, The Small Steps intervention consists of 8-weeks of text messages that integrate diverse evidence-based psychotherapy techniques and brief psychoeducational content to users. Messaging provides brief interactions that serve to keep the psychological strategies and goals in the user's mind, while psychological content, which is also brief, provides context for the messages. The clinical trial design is described below under **Clinical Trial Design**, but briefly the trial will include 3 arms, an active psychoeducational control arm, an *adaptive* version that will use machine learning to personalize message number, timing, and content, and a *randomized* version which will be the same intervention as the adaptive version, but will not use any machine learning or personalization. For individuals randomized to the adaptive or randomized versions of the Small Steps Intervention and who show signs of early disengagement (described below) in the first 2 weeks of use, participants will be re-randomized to receive human supported coaching.

Small Steps Intervention Design

The intervention system consists of interactive messages, which comprise 11 psychological strategies as well as various interaction styles.

Messages:

Please reference Section 8.1.1, 8.1.1.1, and 8.1.1.2, above for a description of messages, psychological strategies, and interaction types that will be used in the Small Steps Intervention Design.

1) Decision Engines:

Adaptive Intervention:

Content types, psychological strategies, message timing, and frequency will be adapted based on a machine learning (multi-arm bandit) algorithm built into the messaging system. Content preferences such as message satisfaction (e.g., 5-pt Likert scale rating of how much the user liked the message/content), engagement rates (e.g., how recently or frequently a user responds to the intervention messages), link clicks (whether a user clicks a link sent in a message) will be used to evaluate content preferences and power the machine learning algorithms.

Randomized Intervention:

The randomized treatment will use the same intervention as the Adaptive Intervention, except that it will not use machine learning for personalization but instead use a randomization engine that will give equal weight to all potential content decisions.

Coaching:

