Coaching involves human provisioned support, typically delivered by telephone or messaging (e.g., email or text). Coaching is believed to work in part by establishing a relationship that provides support and accountability.³⁸ A large number of studies have demonstrated that coaching improves both intervention use²⁰ and mental health outcomes.²⁹ While we expect that our messaging intervention will be engaging, we must also anticipate that there will be a group of users who will not engage. We therefore will explore the potential benefit of adding coaching to our messaging platform. Among those randomized to receive a messaging intervention, participants who become disengaged during the first 2 weeks of the intervention, will be re-randomized at the time they are determined to have disengaged to receive either (a) coaching, to help support engagement, in addition to continued randomized or adaptive messaging, or (b) continued adaptive or randomized messaging via SMS without coaching, depending on the participant's original intervention assignment.

Disengagement will be defined as 3 or more non-continuous days of not responding to messages, rating messages, or completing symptom assessments. Any single action will be considered evidence of continued engagement.

Treatment Arms:

Adaptive Intervention: The adaptive intervention will be powered by reinforcement learning to deliver tailored SMS messages based on user profiles and the ways in which a user interacts with the intervention system, along with links to longer psychoeducational content.

Randomized Intervention: The randomized treatment will use the same intervention as the Adaptive Intervention, except that it will not use machine learning for personalization.

[figure not shown]
Active Control (AC): In the Active Control group participants will receive psychoeducational text messages, (up to 3 on each of the 11 psychological strategies), but these messages will not include interactive messaging (i.e., messages that require a response or action from the user other than reading or clicking on a link to learn more about a particular psychological strategy). Some messages will contain a URL link that contains information about psychological strategies that may be helpful for managing symptoms of depression and anxiety proposed messaging interventions.

Clinical Trial Design:

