The clinical trial will utilize a SMART trial design (see Figure below). Participants will be recruited from MHA's website. The first level of randomization is to one of the three treatment conditions: (1) active control (n=40), adaptive intervention (n=40), or randomized intervention (n=40). This level of randomization will provide us with preliminary data on 1) the effectiveness of messaging as an

intervention and 2) the effectiveness and engagement of randomized vs. adaptive versions. The second level of randomization occurs following disengagement (as defined above under "Coaching" within the first two weeks of intervention use). Participants who meet the disengagement criteria from either the randomized or adaptive intervention will immediately be randomized to receive coaching or continue as self-guided. This data will provide us with preliminary information on the need for and value of coaching (Figure below).

Figure. SMART Trial Design

User feedback: When a participant concludes the intervention (up to 10 participants from each treatment combination [e.g., randomized intervention no coaching; randomized intervention + coaching; adaptive intervention no coaching; adaptive intervention + coaching]), they will be asked to engage in a 30-45-minute user feedback interview, to identify problems and deficiencies with the aim of improving the intervention. Participants who discontinue the intervention will be contacted for an interview at the time their discontinuation is confirmed.

Assessment Strategy:

The primary outcome is psychological distress, measured using the Kessler Psychological Distress Scale (K10).⁴⁹ Administration will occur as part of the research protocol via REDCap online. The primary intervention target is engagement length, measured by time from 1st message sent to the last data point obtained via SMS. Secondary outcomes include: depression, measured by the PHQ-9;³⁹ anxiety, measured by the GAD-7;⁵⁰ suicidal ideation, measured by the DS1-SS;^{51,52} and openness to seeking psychological care, measured by the Attitudes Toward Seeking Professional Psychological Help Scale-Short Form (ATSPPH-SF).⁵³

Data will be gathered from patients as outlined in the table below.

Table of Study Assessments and Assessment points

Construct	Measures	Brief Description	Screening	Study Week						
				0	1	4	8	12	16	

PROTOCOL TITLE: Digital Mental Health Service for Non-Treatment Seeking Young Adults

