General Study management	Group Assignment Check	A single item measure assessing which treatment arm the participant thinks they were in.			X			

Objective Engagement	Phone number and System Use/message Logs			Throughout
----------------------	--	--	--	------------

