If the treatment by time interaction indicates a significant difference between at least one messaging intervention and the control group for a given outcome ($p < .05$), as described in 2a, we will compare the adaptive and randomized messaging interventions for that outcome using the same GLMM approach, restricted to the 2 treatment arms. Outcomes will include the primary clinical outcome measure (K10) and secondary outcome measures (PHQ-9, GAD-7, DSI-SS, CB-RSS). The second primary outcome, engagement duration (time from first message received to last participant interaction), will be summarized descriptively by reporting means and standard deviations, and will be further explored using distribution-appropriate comparisons, as needed.

Aim 2c. Effectiveness of coaching for early disengagement

Participants in the intervention arms who meet predefined criteria for disengagement during the first 2 weeks will be re-randomized to receive coaching or continue without coaching. Analyses will use the same GLMM methods described in Aim 2a incorporating coaching as a covariate to explore whether coaching improves: engagement outcomes (engagement duration, response percentage, number of URL clicks), outcomes (K10, PHQ-9, GAD-7, DSI-SS, CB-RSS). Given the limited statistical power for this embedded re-randomization, results will be summarized descriptively, reporting model coefficients and confidence intervals rather than conducting formal hypothesis tests.

Aim 2d. Exploratory predictors of early disengagement

The need for coaching will be defined as meeting the disengagement criterion during the first 2 weeks. We will compare baseline demographic, clinical, and attitudinal variables between participants who do and do not meet this criterion. Continuous variables will be compared using the Wilcoxon rank sum test, and categorical variables will be compared using Pearson's chi squared test or Fisher's exact test when expected cell counts

are small.

In addition, exploratory predictive models such as random forests will be considered to evaluate whether combinations of baseline variables can classify participants who are likely to disengage early. These analyses are exploratory and intended to generate hypotheses for future trials.

Aim 3. Experimental therapeutics modeling

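### Aim 2c sets no post-re-randomisation window for response percentage or URL clicks and omits logged pre-coaching engagement, which can dilute some coaching contrasts and gives up precision

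*SAP*

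**What the plan says.** SAP Aim 2c names three engagement outcomes for the coaching comparison, in an analysis "incorporating coaching as a covariate to explore whether coaching improves: engagement outcomes (engagement duration, response percentage, number of URL clicks". On the choice of model it says: "Analyses will use the same GLMM methods described in Aim 2a incorporating coaching as a covariate". The Aim 2a model has arm, time, arm by time, a participant random intercept and an autoregressive correlation. Its only other named covariates are baseline demographics, in secondary models. Because power is limited, Aim 2c will report coefficients and confidence intervals without formal tests.

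The one time origin the SAP gives for an engagement measure is under Aim 2b: "engagement duration (time from first message received to last participant interaction". The protocol (section 8.1, Assessment Strategy) is similar: "measured by time from 1st message sent to the last data point obtained via SMS". Neither document gives a window or a denominator for response percentage, or a window for clicks.

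On timing, the protocol's Coaching text says that disengaged participants "will be re-randomized at the time they are determined to have disengaged", and Clinical Trial Design places this within the first two weeks. The trigger is stated as: "Disengagement will be defined as 3 or more non-continuous days of not responding to messages", with ratings and symptom assessments also counting as activity. Treatment length is given by: "The Small Steps intervention consists of 8-weeks of text messages". The assessment table lists objective engagement, from "Phone number and System Use/message Logs", as collected throughout. Section 17.0 says that logs of messages sent and received are downloaded regularly.

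**The concern.** Coaching cannot affect replies or clicks made before a person is re-randomised. If those days enter the outcome, the coefficient for some measures describes a mixture of time when coaching could act and time when it could not.

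Each re-randomised person also has a logged baseline for this comparison, namely their own engagement between the first message and the trigger. The model does not use it, although this is among the smallest comparisons in the trial.

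Coefficients and intervals are all that Aim 2c will deliver. The study is meant to inform a larger SMART, and SAP Aim 3 lists Aims 2a to 2c among the effects on which mediation analysis depends. An understated or needlessly imprecise coaching estimate would carry into both.

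**Working it through.** **The plan's own figure.** The documents give no sample size, power or precision figure for coaching. The nearest is in protocol section 3.0: 80% power at d=0.64 with 40 per group, for treatment versus control. It reproduces (80.7% by noncentral t, 81.7% by normal approximation, two-sided 0.05) but has no bearing on Aim 2c.

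**Inputs from the documents.** Treatment lasts 8 × 7 = 56 days. The trigger day t is day 3 at the earliest and about day 14 at the latest. If the word non-continuous strictly rules out consecutive days, the earliest trigger is day 5.

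**Assumptions.** The documents do not give the number re-randomised, the correlation between earlier and later engagement, the share of clicks made before the trigger, or the SD of duration. Ranges are used below.

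**Response percentage over 56 days, roughly even messaging.** The pre-trigger part has the same expectation in both coaching groups, so the whole-period difference is (56−t)/56 of the post-re-randomisation difference.

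- t=3: 53/56 = 94.6%
- t=5: 51/56 = 91%
- t=7: 49/56 = 87.5%
- t=14: 42/56 = 75.0%
- t uniform on days 3–14 (mean 8.5): 47.5/56 = 85%

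**URL clicks.** In an absolute difference, the pre-trigger clicks cancel in expectation. On a ratio scale, with s the share of uncoached participants' clicks made before the trigger, the observed ratio is s + (1−s)RR. For a true RR of 1.5:

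- s=5%: 0.05 + 0.95×1.5 = 1.475
- s=25%: 0.25 + 0.75×1.5 = 1.375
- s=50%: 0.50 + 0.50×1.5 = 1.25

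**Engagement duration.** Duration equals t plus the time from re-randomisation to the last interaction. Since t has the same distribution in both groups, it cancels from the mean difference. It only adds spread. With t uniform on days 3–14, its SD is √((12²−1)/12) = 3.45 days. If time after re-randomisation has an SD of 10 to 20 days, the total SD rises by a factor √(1+(3.45/10)²) = 1.058 to √(1+(3.45/20)²) = 1.015.

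**Precision from a prior measure.** In large samples the standard error is multiplied by √(1−ρ²): 0.95, 0.87 and 0.71 at ρ = 0.3, 0.5 and 0.7. In small samples the extra covariate has a cost. Simulation compared coaching plus arm with coaching plus arm plus one prior measure, for 8 to 20 per coaching arm:

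- ρ=0.3: mean interval width changes by about 0 to −3%
- ρ=0.5: about −9 to −12%

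Adding trigger day as well, at ρ=0.3, makes the interval about 6% wider at 8 per arm and 1% wider at 12.

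**Why prior engagement and trigger day overlap.** If re-randomisation follows immediately on the third inactive day, active days before it number t−3. The active share is then 0/3 = 0 at day 3, 4/7 = 57% at day 7 and 11/14 = 79% at day 14. At day level, trigger day fixes prior activity. Message-level response percentage can differ somewhat from this.

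**Both parts together.** An illustrative simulation of response percentage used 20 per arm, triggers uniform on days 3–14 and a correlation of about 0.56:

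| Analysis | Coaching difference | SE |
|---|---|---|
| Whole period | 0.124 | 0.071 |
| After re-randomisation | 0.147 | 0.074 |
| After re-randomisation, adjusted | 0.147 | 0.060 |

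The window corrects the size of the effect. The adjustment supplies the precision.

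**The case against.** A reader might infer that all three engagement outcomes are diluted. The documents do not support that: coaching is randomised, so pre-coaching engagement cancels from the mean difference in duration and from an absolute difference in clicks.

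A reader might also infer that the SAP commits to counting pre-coaching replies and clicks. It does not; it is silent. A whole-period percentage is, moreover, a legitimate randomised contrast for engagement over the full 8 weeks, so choosing the later window is a choice of estimand. Both points stand. However, Aim 2c asks whether coaching improves engagement, and the post-re-randomisation window answers that more directly.

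It can be said that modelling weekly values would let the random intercept absorb prior engagement. With coaching entered as a time-constant covariate, it does not remove the dilution. In a simulated weekly model with a true effect of 0.15, the coaching coefficient averaged 0.127, which is 85%. Coding coaching as time-varying could help, but the SAP does not specify it.

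Even messaging is doubtful in the adaptive arm, where message timing and frequency adapt. The (56−t)/56 figures are therefore approximate; with uneven messaging, the share of messages sent before the trigger takes the place of t/56.

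Finally, the prior period is short and shaped by the trigger rule, so nothing in the documents supports a particular correlation. That stands, and it is why the precision gain is given only as a range.

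**Conclusion.** The point holds in a limited form. Aim 2c leaves the window open for two outcomes and leaves out a baseline that is already collected.

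A whole-period response percentage would understate the coaching difference by about 5 to 25%, or about 15% on average if triggers fall evenly over days 3–14. This assumes roughly even messaging. A click ratio would be pulled toward 1 by an amount that depends on the unknown share of early clicks. Duration in days and absolute click differences are not diluted.

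The precision given up ranges from nothing to about 12% of interval width over the correlations of 0.3 and 0.5 and the 8 to 20 per coaching arm assumed here.

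It is tempting to turn this into a gain in power, but the documents do not support that. Aim 2c makes no formal tests, d=0.64 belongs to treatment versus control, and the number re-randomised is unknown. The feasibility criteria are unaffected. The consequence is confined to the coefficients and intervals of Aim 2c and any later use of them.

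**What to change.** In SAP Aim 2c, for re-randomised participants:

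- Compute response percentage (with its denominator stated) and URL clicks from re-randomisation to the end of week 8.
- Regress each on randomised coaching, first-stage arm and the same measure before re-randomisation. Do not also add trigger day, because the two largely overlap under the three-inactive-day rule.
- Report the coaching coefficient with its 95% confidence interval, and attach no power claim.
- State whether duration keeps its first-message origin or is counted from re-randomisation.

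The cost is a few sentences in the SAP, a date cut in existing message logs and one degree of freedom. If few people are re-randomised and the correlation is low, the adjustment brings little or no gain in precision.

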2. Clinical Trial – With 40 participants randomized to each group, we will have 80% power to detect an effect size of $d=0.64$ for the treatment vs. control compassion. The effect sizes related to messaging interventions for depression have not yet been tested across enough trials to estimate effect sizes. However, meta-analyses comparing coached DMHIs to control conditions have shown effect sizes of $gs=0.67-0.70$ for depression and anxiety, which is not significantly different from psychotherapy.⁴¹ Effect sizes for self-guided DMHIs and smartphone interventions are considerably smaller ($gs=0.27-0.43$).^{42,43} It should be noted that choice of control condition can have a substantial impact on effect sizes. For coached DMHIs, the effect-size for trials using WLCs is $g=0.90$, while effect sizes for studies using active controls is understandably smaller, $g=0.38$.⁴¹ Thus, we would expect to see an effect size of approximately $d=0.38$ for treatment vs. control, as these analyses will pool participants across both engaged participants, who do not require a coach, and coached participants. While we acknowledge this effect size is lower than the effects we are powered to detect, it serves as a useful benchmark in determining whether the intervention shows sufficient value to pursue a larger trial.

As the use of machine learning to personalize messages is novel, there are no studies that provide ideal guidance as to the expected effect size for the adaptive vs. randomized intervention comparisons for DMHIs. However, there is considerable research using “computer-tailored” messaging for health behaviors (e.g. smoking cessation, physical activity, diet, mammography). A meta-analysis showed effect sizes of $g=0.12-0.22$ for tailored vs. randomized messaging.³⁵ These algorithms are simpler than those proposed here, typically consisting of decision trees that tailor only on baseline participant characteristics. Based on this literature, we would expect an effect size of approximately $d=0.20$ in analyses comparing the randomized and adaptive arms. Such an effect size would warrant the inclusion of the proposed machine learning algorithms to personalize messages to meet the needs and preferences of users.

- a. Active Control Group (n=40)
- b. Automated Intervention (n=40)
- c. Randomized Intervention (n=40)

4.0 Recruitment and Screening Methods:

(1) Longitudinal Usability Testing:

The sample will be recruited from two sources:

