Statistical Analysis Plan for clinicaltrials.gov

Official Title: Digital Mental Health Service for Non-Treatment Seeking Young Adults

NCT Number: NCT04948268

Grant Number: R34MH124960

Northwestern University Social and Behavioral Institutional Review Board Number: STU00214822

Statistical Analysis Plan

Aim 2. Feasibility

The primary aim of this study will be to evaluate the feasibility of conducting a larger SMART trial. Feasibility will be determined by:

1. meeting recruitment and enrollment goals;
2. obtaining at least 80% of follow up self-report data at primary endpoints; and
3. maintaining dropout below 30% across treatment conditions.

Descriptive statistics will be used to summarize recruitment, retention, completeness of self-report measures, and patterns of missing data. These analyses will inform the suitability of procedures for a future fully powered trial.

Aim 2a. Effectiveness of messaging interventions relative to active control

To evaluate the effects of the adaptive and randomized messaging interventions relative to the control condition, we will model trajectories of the primary outcome (psychological distress; K10) and secondary outcomes (PHQ-9, GAD-7, DSI-SS, and CB-RSS). For each outcome, we will estimate a generalized linear mixed model (GLMM) with one model per outcome, fixed effects for treatment arm, time, and the treatment by time interaction, a participant-level random intercept, an autoregressive correlation structure for repeated observations, and an identity link for normally distributed outcomes, with alternative link functions used as appropriate based on distributional properties. The primary inference will focus on the treatment by time interaction to determine whether either intervention produces a different rate of change over time compared to control. Secondary models will control for baseline demographic covariates (e.g., age, sex, race, ethnicity).

Controlling for missing data and bias. Should more than 5% of the outcome data be missing, we will examine the data for missing mechanisms and use multiple imputation rather than complete case analysis for the primary analysis to avoid bias, combining results from 5 imputed datasets using “mice”.

Aim 2b. Effectiveness of adaptive versus randomized messaging

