We will explore whether engagement targets (engagement) and psychological targets (coping skill use; CB-RSS) mediate treatment effects on psychological distress outcomes (K10) and secondary outcomes (PhQ-9, GAD-7, DSI-SS). Mediation analyses will be conducted only if the necessary preconditions for mediation are met (e.g., a significant effect of intervention condition(s) on the outcome (Aims 2a-2c), and a significant effect of intervention condition(s) on the proposed target (engagement or coping skill use; CB-RSS)).

If these conditions are met for an outcome/target pair, we will use generalized linear models to estimate paths a (intervention to target) and b (target to outcome) using appropriate link functions based on variable distributions. Mediation will be evaluated using the Iacobucci method, which constructs a normally distributed test statistic from standardized regression coefficients. Because these analyses are exploratory and involve multiple parallel models, we will control the false discovery rate (FDR) using the Benjamini-Hochberg procedure, with an FDR threshold of 10% appropriate to pilot mediation work. If the prerequisite conditions are not met for a given mediator or outcome, mediation models for that pair will not be estimated.

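### SAP Aim 3 treats the mediation statistic as normally distributed, but with about 40 per arm it is under-dispersed unless one path is very strong, so the test is conservative and will miss real mediators

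*SAP*

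**What the plan says.** SAP Aim 3 asks whether engagement and coping skill use (CB-RSS) mediate treatment effects on K10, PHQ-9, GAD-7 and DSI-SS. "Mediation analyses will be conducted only if the necessary preconditions for mediation are met": the intervention must affect the outcome significantly, and there must be "a significant effect of intervention condition(s) on the proposed target". Pairs that pass go to generalized linear models for path a (intervention to target) and path b (target to outcome), with link functions chosen by distribution. The test is then described: "Mediation will be evaluated using the Iacobucci method, which constructs a normally distributed test statistic from standardized regression coefficients". Multiplicity is handled by Benjamini-Hochberg, "with an FDR threshold of 10% appropriate to pilot mediation work". The section calls the work exploratory. It gives no path sizes, no power for mediation, no separate 5% level for this test, and no interval for the indirect effect.

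The only power statement is in Protocol section 3.0: 40 per group gives 80% power for d = 0.64, while about d = 0.38 is expected for treatment versus control. SAP Aim 2 sets a target of 80% follow-up completeness.

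**The concern.** A product of two estimates divided by its delta-method standard error approaches a standard normal only when at least one path is large relative to its standard error. With 40 per arm and moderate paths, the product is skewed and peaked and its ratio is too tightly concentrated around zero. P-values read from the normal table are then too large, and these p-values enter the Benjamini-Hochberg step.

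Aim 3 is meant to identify targets worth carrying into a larger trial. By relaxing the false discovery rate to 10%, the SAP signals that missed mediators are the costlier error at this stage. A conservative test works against that choice, and it does so after each pair has already passed two significance gates.

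**Working it through.** **Inputs from the documents.** 40 per arm; 80% completeness, which leaves 32 per arm; Benjamini-Hochberg at 10%; two gates before testing; two kinds of target and four outcomes.

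**Assumptions.** Standard Iacobucci form, z = za·zb/√(za² + zb² + 1), where za and zb are the path estimates over their standard errors. Gates at two-sided 5%. Path sizes a (in SD) and b are varied, because the documents give none. Outcomes are linear and normal, with one mediator, one time point and complete data.

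**Step 1: the plan's own figure.** For d = 0.64 and 40 per arm, the expected z is 0.64 × √(40/2) = 2.86, and Φ(2.86 − 1.96) = 81.7%. The t-test version is 80.7%. The stated 80% is reproduced.

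**Step 2: algebra, needing no path sizes.** Since zb² < za² + zb² + 1, |z| is always below |za|, and by symmetry below |zb|. The mediation p-value therefore always exceeds the path-a p-value that passed the gate (normal reference). To reach a critical value c:

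|zb| > c·√[(za² + 1)/(za² − c²)]

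| za | zb needed, 5% cut (c = 1.96) | zb needed, 10% cut (c = 1.645) |
|---|---|---|
| 2.0 | √(3.84 × 5 / 0.158) = 11.0 | √(2.71 × 5 / 1.29) = 3.2 |
| 2.5 | √(3.84 × 7.25 / 2.41) = 3.4 | √(2.71 × 7.25 / 3.54) = 2.35 |

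**Step 3: spread under the null (40 v 40).** The SD of z is 0.43 with both paths null. With b = 0 it is 0.82 at a = 0.634, 0.92 at a = 1.0 and 0.99 at a = 2.0. A standard normal has SD 1.

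**Step 4: type I error at nominal 5% (40 v 40, b = 0).**

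| a (SD) | No gate | After path-a gate |
|---|---|---|
| 0 | 0.01% | – |
| 0.38 | 0.14% | 0.4% |
| 0.64 | 1.0% | 1.2% |
| 1.0 | 2.8% | 2.8% |
| 1.5 | 4.2% | 4.2% |
| 2.0 | 4.8% | – |

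With both gates it is 1.3% at a = 0.634 and 2.9% at a = 1.0. With a = 0 and no gate it is 1.7% at b = 0.39 and 3.7% at b = 0.59. With 32 v 32 and a = 0.64, no gate, it is 0.8%. A percentile bootstrap after the path-a gate gives 4.4% to 6.3%.

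**Step 5: share of bootstrap detections missed at a 5% cut (no gate).**

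| a | b | 40 v 40 | 40 v 80 (arms pooled) |
|---|---|---|---|
| 0.38 | 0.30 | 61% | 45% |
| 0.50 | 0.39 | 33% | – |
| 0.64 | 0.30 | 41% | 20% |
| 0.64 | 0.39 | 23% | 9% |
| 0.64 | 0.50 | 10% | – |
| 1.0 | 0.39 | 5% | – |

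After the path-a gate, the 40 v 40 range is 5% to 59%. With 32 v 32, a = 0.64 and b = 0.30, the ungated figure is 51%.

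**Step 6: the SAP's actual criterion.** Two kinds of target times four outcomes gives up to 8 pairs per contrast. Under Benjamini-Hochberg at 10%, a lone true mediator among m tested pairs must meet 0.10/m: 5% for 2, 2.5% for 4, 1.25% for 8. If one pair is tested, or every tested pair falls below 10%, the cut is 10%. Power after both gates at a = 0.634, b = 0.32, with ranges across separate runs:

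| Per-test cut | Iacobucci | Monte Carlo |
|---|---|---|
| 10% | 74% | 84–87% |
| 5% | 50–51% | 74–78% |
| 2.5% | 30% | 64% |
| 1.25% | 14–15% | 49–53% |

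With a very strong path (a = 1.5, b = 0.32, 5% cut), the figures are 76% against 78–80%.

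**The case against.** The strongest defence has four parts.

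- **The criterion is a 10% false discovery rate, not a 5% test.** If one pair is tested, or all tested pairs qualify, the cut is 10% and the loss is modest: 74% against 84–87% power in the scenario above. This stands, but only for those cases. When several pairs are tested and few are real, the cut falls and the loss grows.
- **Path a may be strong.** The protocol's active control has no interactive messaging, so a messaging-versus-control contrast on engagement could be large, and the gates favour large path-a estimates. This also stands. At a = 1.5 SD the problem nearly vanishes, but the documents do not say the path is that strong. For coping skill use, nothing in them suggests it.
- **The error is in the safe direction and the aim is exploratory.** This stands. Larger p-values do not inflate false discoveries, and feasibility is the trial's primary aim.
- **A bootstrap of a·b is not a drop-in replacement.** The SAP allows different links for the two paths, so a raw product need not lie on one scale. Resampling would also have to be combined with the five imputed datasets if imputation is used here. This stands against a raw-product interval in every case. It does not stand against a Monte Carlo distribution of za·zb, which uses only the standardized paths.

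**Conclusion.** The point holds as a matter of conservatism. At about 40 per arm the statistic is not standard normal unless one path is very strong. Type I error at nominal 5% lies between near 0% and nearly 5%. At a 5% cut, roughly 5% to 60% of the effects a bootstrap detects are missed. At the 1.25% cut that eight pairs can impose, power in one moderate scenario is 14–15% against 49–53%.

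A reader might infer three stronger things that the documents do not support:

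- **That the true error rate is under 1%.** This is so only when both paths are null or the non-null path is weak. After the SAP's gates it is already 1.2–1.3% at a ≈ 0.64 and just under 3% at a = 1.0.
- **That about a third of mediators are lost.** That is one point (a = 0.5, b = 0.39) in a wide range, and the documents give no path sizes to select it.
- **That Aim 3 would yield false mediators or disturb a primary result.** The error runs the other way, and nothing primary depends on this test.

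The figures rest on the standard form of the statistic and on the linear, complete-data, single-time-point model. The SAP's mixed models and multiple imputation were not simulated. The change is worth making because it is cheap, but the matter is of moderate weight.

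**What to change.** In SAP Aim 3, delete the statement that the statistic is normally distributed and specify instead:

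- The p-value entering the Benjamini-Hochberg step comes from a Monte Carlo distribution of the product of the standardized paths, with at least 5,000 draws. Draw za* from N(za, 1) and zb* from N(zb, 1), form za*·zb*, and double the smaller share of draws on either side of zero. A percentile bootstrap with at least 5,000 draws is an acceptable alternative.
- Where both paths use an identity link, the indirect effect a·b is also reported with its 95% Monte Carlo or bootstrap interval.
- If imputed data are used, the Monte Carlo step is applied to the pooled path estimates and their pooled standard errors.

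The cost is a few SAP sentences and a few lines of code, with no new data. One drawback should be stated in the SAP: after gating, size can sit slightly above nominal, at about 5–6% for a 5% test.
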